Quasi-Desensitization Placebo Therapy (QDT). This form of placebo therapy has been commonly used in prior studies investigating behavioral interventions for insomnia^{9,13,51,52}. The therapist presents the QDT as a means to eliminate "conditioned arousal," occurring after nocturnal arousal using 8 sessions on a weekly basis. The therapist initially helps the subject to develop a chronological 12-item hierarchy of commonly practiced activities on awakening at night, like opening eyes and clock watching. As a next step, the subject develops 6 imaginal scenes of himself/herself engaged in neutral activities like reading a newspaper. The therapist then helps the subject pair the neutral scenes with the items from the 12-item hierarchy, which is then practiced by the subject ≥ 2 hours before bedtime.

- 2.2. Describe how randomization or other treatment assignment will be made. **Subjects will be block randomized using a computer generated randomizing sequence.** Participants are randomly assigned to the CBT-I group, or the QDT group. The study biostatistician will create randomization sequences by family history of alcoholism (separate sequences) using a pseudo-random number generator with block sizes of 4. Two boxes of sequentially numbered, sealed, opaque envelopes will be prepared using the randomization sequences and labeled "Family History" and "No Family History". At the time of randomization, the first envelope, in sequential order, is pulled from the appropriate box and opened to reveal the group assignment. All the staff conducting assessments will be blinded to the allocation of treatment arm with the exception of Dr.

[name], the BSM treatment provider, [name] the person overseeing treatment allocation, and [name], the monitor for BSM treatment for the study.

- 2.3. For retrospective research studies, provide the "look-back" period. (e.g., December 1, 1999 through December 31, 2008.) **N/A.**

3. **Study Duration**

- 3.1. Provide the estimated length of time to enroll all subjects and complete the study. **Five years.**
- 3.2. Explain the expected duration of subject participation including any follow-up. **Eight months.**
- 3.3. Specify the projected date of completion of the proposed study. **Dec. 2018.**

4. **Drug Information.** Not Applicable.

5. **Investigational Device.** Not Applicable.

M. **Does this project involve international research?** YES NO

N. **Study Procedure.** Please see Table 1 for all the study-related procedures.

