
early phases of the study, using laboratory data, inclusion and exclusion criteria, and other person-specific information). Personnel involved will include the following: Principal investigator, study coordinator, behavioral sleep medicine practitioners associated with this study.

- 9.5.6. Include the breakdown of each individual's responsibilities:
 - 9.5.6.1. **Principal Investigator.** He may fulfill any of the roles required for the study, including, answering questions for prospective participants, informed consent procedure for participation for assessment for study entry, baseline assessments, assessments as part of the study visits, conducting the cognitive behavioral therapy sessions, scheduling the participant sessions, post-study assessments, conducting the urine drug screens, drawing blood and preparing the blood sample for storage in the freezer, coordinating clinical care with other providers.
 - 9.5.6.2. **Co-Principal Investigator, N/A**
 - 9.5.6.3. **Research Coordinator.** S/he will be involved in answering questions for prospective participants, informed consent procedure for participation for assessment for study entry, baseline assessments, assessments as part of the study visits including the urine drug screen test at baseline, drawing blood samples (after completion of the requisite training), scheduling the participant sessions, post-study assessments.
 - 9.5.6.4. **Additional research staff by title.** a. Phlebotomy – either [name] or a designated staff certified and IRB-approved to draw blood will conduct the blood draws and prepare the samples for the storage in the designated R & D freezer space; b. Certified Behavioral Sleep Medicine Provider: s/he will conduct the CBT-I and the QDT sessions for the participants; the Principal Investigator, [name] will conduct CBT-I or QDT as a backup provider.
- 9.6. Will informed consent be obtained from potential subjects prior to determining eligibility?
 YES NO N/A
 - 9.6.1. If no, provide justification and a HIPAA Waiver of Individual Authorization for Disclosure of Protected Health Information.
- 9.7. **Define when a subject is enrolled into the study, e.g. after the subject signs the informed consent or after randomized to treatment.** After he is randomized into a treatment arm.
- 9.8. Describe:

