 - e. Confidentiality: During the participation in this study, the patient will be assigned a 4-digit unique identification number. This number will not be derived from PHI of any sort (e.g., DOB, SSN, etc.) and will simply represent the study and the subject's recruitment number (e.g., 1001). Study numbers will be linked to subject identifiers in one spreadsheet that will be stored on the PI's password-protected VA online drive. These efforts make it very unlikely that the subject's identifying data and/or study

information may be viewed by non-study personnel. The data will now be captured and stored within the VA Redcap and stored in the secured VA servers.

- f. Relapse to the Drinking. All drinking behavior will be monitored. Monitoring will be based upon self-report items on the daily sleep diaries and clinical interviews by the principal investigator during the outpatient visits. These variables will be monitored for both research and clinical purposes. The research purpose is to determine how alcohol use varies with treatment for insomnia. The clinical purpose is to be able to determine if there has been a resumption of heavy drinking (four standard alcoholic drinks on any day or ≥ 14 drinks a week). If there is a resumption of sustained heavy drinking and this sustained heavy drinking places the subject at risk of medical, psychological or physical harm, then he will be withdrawn from the study, and a referral to the ARU or the inpatient unit, as deemed necessary for further treatment, will be offered to the participant
- g. Use of Other Street Drugs. Patients will be evaluated for the use of other street drugs through structured assessment instruments. Further, if there is a history of regular drug use, the subject will be regularly monitored with standard urine tests (note: this will be a condition for admittance into the study). If regular drug use is detected, the subject will be withdrawn from the study, and a referral to the ARU for further treatment will be offered to the participant.

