- 4.2. **Define plans for data and statistical analysis, including key elements of the statistical plan, stopping rules and endpoints.** *Overview:* Our study proposes a longitudinal repeated-measures parallel-group design. This powerful design, with a baseline measurement and up to ten follow-up measures per participant over 6 months, allows for comparisons within each participant over time as well as across participants (treatment groups). The main analysis will look at differences between intervention groups in the changes in outcomes over time (i.e. insomnia severity, alcoholism-related outcomes and daily functioning). *Randomization:* Patients will be recruited and randomized as individuals. Allocation will be uniform across the two groups after suitable blocking and stratification on family history of alcoholism to ensure optimal balance of participant characteristics and to observe relationships between groups with and without a family history of alcoholism in the Exploratory Aim. Participants are randomly assigned to the CBT-I group, or the QDT group. The study biostatistician will create randomization sequences by family history of alcoholism (separate sequences) using a pseudo-random number generator with block sizes of 4. Two boxes of sequentially numbered, sealed, opaque envelopes will be prepared using the randomization sequences and labeled "Family History" and "No Family History". At the time of randomization, the first envelope, in sequential order, is pulled from the appropriate box and opened to reveal the group assignment. All the staff conducting assessments will be blinded to the allocation of treatment arm with the exception of [name], the BSM treatment provider, [name] the person overseeing treatment allocation, and [name], the monitor for BSM treatment for the study. *Preliminary Analyses:* All data, regardless of the format, will first be assessed by [name] and his mentors for missing data, distributions of all observed measures, and out-of-range values by means of conventional descriptive tables. SAS v9.3 will be our primary tool for these analyses as the software is both mature and well-documented⁵⁶. Next, we will employ raw and smoothed plots to visualize the individual and average trajectories of all repeated measures over time according to assigned treatment and by participant characteristics. All questions of data quality and integrity will be investigated before any statistical modeling, since complete and accurate data are essential for unbiased estimates and confidence intervals. We will compare all baseline variables across groups to check the adequacy of randomization. The baseline comparisons will be based on: 1) t-test or Wilcoxon rank sum tests for continuous variables depending on the symmetry of the distributions; 2) on logistic regression for binary or ordinal variables; and 3) on Poisson log-linear regression for count data. If imbalances are found at baseline, then the relevant variables will be treated as confounders in the analysis.

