- 5.1. If yes, clearly explain how participants will be contacted. We will contact the prospective participants who have been identified by their providers after expressing willingness regarding the study or alternatively, if the participant contacts us directly regarding the study. In addition, providers of patients identified by review of records will be contacted by the study related staff to discuss the study briefly with the patients.
6. Provide the titles of the exact individuals who will have access to the collected data. See section 6.1 below for details.
- 6.1. Explain why these individual will have access to this data.
1. The principal investigator – he may conduct any of the procedures, as may be necessary
 2. Research Assistant – coordinate the study related visits and procedures.

3. Psychologist associated with the study (Certified Behavioral Sleep Medicine Specialist, TBA) – to assess, and answer any questions that the participant may have, especially if he is non-compliant with a study related visit.
4. The regulatory agencies including the IRB at the CMCVAMC, DMC, and the grant funding organization VA CS R & D. They will have access to the information in order to conduct their regulatory activities.
5. The genetic data will be stored in the freezer space designated by the CMCVAMC R & D services and will reside there with the coded identification numbers and without any of the 17 HIPAA identifiers. Once all the samples have been collected and we are ready to commence the genetic analyses, we will request CMCVAMC -IRB approval to transfer the blood samples to the designated laboratory at the University of Pennsylvania for further analyses of the samples. After the analyses the blood samples will be destroyed.

X. Information Security

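### Blinded assessment of the primary alcohol outcome is not assured: no rule stops treating or unblinded staff, including the principal investigator, from assessing outcomes

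*Combined protocol and SAP*

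**What the plan says.** **Blinding.** Sections L.2.2, N.2.1.2 and V.4.2 carry the same sentence: "All the staff conducting assessments will be blinded to the allocation of treatment arm with the exception of" certain people. Those people are identified by name (removed in the public text) and by function: the behavioral sleep medicine treatment provider, the person overseeing treatment allocation, and the monitor of treatment.

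**Principal investigator's roles.** Section Q.9.5.6.1 lets him fill any role in the study and lists "assessments as part of the study visits, conducting the cognitive behavioral therapy sessions", along with baseline and post-study assessments. Section Q.9.5.6.4 gives the therapy in both arms to a certified provider and adds that the investigator "will conduct CBT-I or QDT as a backup provider". Section W.6.1, on access to data, says of him: "he may conduct any of the procedures, as may be necessary".

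**Drinking data.** Section J defines the primary alcohol outcome as percentage days abstinent, measured with the TLFB. Section T.1.2.f bases the monitoring of drinking on sleep-diary items and "clinical interviews by the principal investigator during the outpatient visits", and adds: "These variables will be monitored for both research and clinical purposes".

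**Data collectors.** Section N.2.1.5 answers a single question about who collects and who analyses the data. Its list includes both the principal investigator and the behavioral sleep medicine provider.

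**The concern.** Blinding the assessor is the main protection available here. Participants know which therapy they are receiving and the therapist necessarily knows the arm, so the person recording the outcome is the one party who can be kept unaware. For recalled drinking this matters in two ways. An interviewer who knows the arm may probe differently, and a participant may answer differently when the questioner is also his therapist.

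A difference of this kind between the arms goes straight into the Aim 2 contrast. The mixed model in V.4.2 adjusts for family history of alcoholism and for baseline imbalances. It has no term for the assessor or the assessor's blinding status, so it would not remove such a difference.

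**Working it through.** No plan figure needs reproducing. The check sets the role descriptions beside the blinding statement and asks whether any rule keeps treating or unblinded staff away from the outcome.

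1. **Can one person both treat and assess?** Yes. Q.9.5.6.1 puts therapy, visit assessments and post-study assessments in one person's list. Q.9.5.6.4 confirms the therapy role in either arm, and W.6.1 excludes no procedure.

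2. **Does the blinding sentence prevent it?** The names are removed, so there are two cases.
   - *The investigator is not among the exceptions.* He should then be blinded, but once he acts as backup therapist he knows the allocation of anyone he treats. If he also assesses that participant, the sentence is breached.
   - *The investigator is among the exceptions.* The sentence and the role list are then consistent. But he is openly unblinded and still permitted to assess.

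   In both cases the sentence says who is unblinded, not that those people stay away from outcomes. No other section says so either.

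3. **Does the gap reach the alcohol outcome?** No section names who administers the TLFB after randomisation. N.2.1.2 says most measures involve interviews. N.2.1.1 and N.2.1.2 allow the research team to complete instruments by telephone and do not themselves require a blinded caller. T.1.2.f gives the investigator's drinking interviews a research purpose, namely how alcohol use changes with insomnia treatment, which is the subject of Aim 2. No text keeps those interviews apart from the TLFB record.

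4. **How large could the effect be?** For each arm, let p be the share of TLFB assessments made by unblinded staff and s the mean shift in reported percent days abstinent in those assessments. Then

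   bias in the arm difference = p(CBT-I) × s(CBT-I) − p(QDT) × s(QDT).

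   The documents give neither p nor s. Each p may lie anywhere from 0 to 1. If both are 0, the bias is 0 × s(CBT-I) − 0 × s(QDT) = 0. If both are 1, it is s(CBT-I) − s(QDT), which is unknown. The 7.98-point detectable difference for abstinent days in V.4.1 is therefore no yardstick: there is no estimate to set against it.

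**The case against.** The best defence is that the role list is permissive and general, while the blinding rule is specific and stated three times. The certified provider is the regular therapist and the investigator only a backup, so the list can be read as subject to the rule. This stands in part. A reader might infer that the blinded-assessor statement is false, but the documents do not support that. A breach is certain only for a participant whom the investigator both treats and assesses while not an excepted person, and no frequency is given.

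A reader might also infer that the TLFB is an interview conducted by the investigator. The documents say neither. T.1.2.f does not mention the TLFB, N.2.1.2 says only that most measures involve interviews, and mailed completion of questionnaires is allowed. The link to the primary alcohol outcome is that nothing excludes it.

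Nor would any bias be wholly untraceable. Sections N.2.1.3 and X.2.1 say that staff enter data directly into REDCap, which logs who enters and alters data. That helps, but it misses paper forms used before the move to REDCap and entries made by someone other than the interviewer.

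Finally, the study coordinator's own blinding is not confirmed, because the person overseeing allocation is not identified in the public text. This limits the remedy but does not remove the gap.

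**Conclusion.** The point holds as a gap in protection. Under the plan as written, treating or unblinded staff may collect the self-reported Aim 2 outcome, so its blinded assessment is not assured. This could bias the comparison of percent days abstinent; the documents do not show that it does. No size in percentage points can be defended, and the effect may be zero if the investigator never both treats and assesses the same participant, provided the other unblinded staff do not assess either.

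The conclusion rests on the role lists being read as they stand and on no separate delegation document closing the gap. It does not depend on whether the investigator is one of the excepted persons. The change should be made because the protocol already promises this blinding and securing it takes little.

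**What to change.** - **Rule.** In L.2.2, N.2.1.2, Q.9.5.6 and V.4.2, state that nobody who has treated a participant or knows that participant's allocation administers the TLFB, the Penn Alcohol Craving Scale or any other outcome instrument to that participant after randomisation, in person or by telephone. Say expressly that this covers the principal investigator as backup provider.
- **Assessor.** Assign these assessments to the study coordinator, whom Q.9.5.6.3 already lists for baseline, visit and post-study assessments, or to another listed blinded staff member. Confirm that this person is not the one overseeing allocation.
- **Drinking interviews.** Keep the investigator's interviews for monitoring as planned, but state that they are not a source for the TLFB outcome.
- **Record and analysis.** Record the assessor of each TLFB, and pre-specify in V.4.2 a sensitivity analysis that excludes assessments made by unblinded staff.

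The cost is protocol wording, one extra data field and slightly less scheduling flexibility. No new staff are needed if the coordinator or another listed person is confirmed as blinded; if none is, the sponsor would have to name someone who is.

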9.9. Provide the language

9.9.1. **Used by those obtaining consent.** English

9.9.2. **Understood by the prospective participant or the legally authorized representative.** N/A

9.10. **Provide location where informed consent will be obtained.** The informed consent session will be conducted in any available private office space available on the 7th or 2nd floor (mental health clinic/ARU clinic), MIRECC office spaces (room # 228), the inpatient units on the 7th floor, or in any available office space in the primary care clinics.

10. **Waiver or Alteration of Informed Consent Requirements/Waiver of Requirement to Obtain Documentation of Informed Consent**

10.1. Are you requesting a waiver or alteration of informed consent? (*Check all that apply*)

10.1.1. No

10.1.2. Yes; provide justification.

10.1.3. Yes; for recruitment purposes only.

10.1.3.1. An IRB may approve a consent procedure which **does not include, or which alters**, some or all of the elements of informed consent set forth in this section, or waive the requirements to obtain informed consent provided the IRB finds and documents that:

- 1. The research involves no more than minimal risk to the subjects;
- 2. The waiver or alteration will not adversely affect the rights and welfare of the subjects;
- 3. The research could not practicably be carried out without the waiver or alteration; and
- 4. Whenever appropriate, the subjects will be provided with additional pertinent information after participation
- 5. The research or demonstration project is to be conducted by or subject to the approval of state or local government officials and is designed to study, evaluate, or otherwise examine:
 - a. Public benefit or service programs;
 - b. Procedures for obtaining benefits or services under those programs;
 - c. Possible changes in or alternatives to those programs or procedures; or
 - d. Possible changes in methods or levels of payment for benefits or services under those programs.

10.2. **Are you requesting a waiver to obtain documentation of informed consent?**

10.2.1. No

10.2.2. Yes; provide justification.

10.2.2.1. An IRB may **waive the requirement for the investigator to obtain a signed consent** form for some or all subjects if it finds either:

- 1. That the only record linking the subject and the research would be the consent document and the principal risk would be potential harm resulting from a breach of confidentiality. Each subject will be asked whether the subject wants documentation linking the subject with the research, and the subject's wishes will govern; or
- 2. That the research presents no more than minimal risk of harm to subjects and involves no procedures for which written consent is normally required outside of the research context.

R. Compensation

1. **Summarize any financial compensation that will be offered to subjects.** Please see Table 3 below for details on the financial compensation.

2. **Provide the schedule for compensation.** The schedule of pro-rated compensation will involve one payment for completion of the baseline assessments measures, weekly compensation for the each of the study visits over 8 weeks, and for the 2 post-study visits at 3 months and 6 months.

2.1. **Per study visit or session.** The specific details of the payments are shown in Table 3

2.2. **Total amount for entire participation.** \$750.

3. **Explain how compensation will be provided via cash, voucher, gift card, etc.** Patient will be given a voucher that may be exchanged for cash at the agent cashier of CMCVAMC, similar to that done for prior studies.
4. **If financial compensation will be prorated, explain the process.** See Table 3 below for details.
5. Not Applicable -

Table 3: Suggested Pro-rated Financial Compensation Involved with

Missing Assessments	Baseline Assessments	Week 1-7	Week 8	F/U (in 3 & 6 months)
None	\$150	\$50	\$100	\$75
Incomplete Actigraphy	\$125	\$25	\$75	\$40
Incomplete forms	\$125	\$25	\$75	\$50
≥ 2 Rating Scales	\$125	\$20	\$70	\$40
Polysomnogram	\$100	-	\$50	-
Any combination of above	\$50	\$15	\$15	\$40
No blood sample	\$100	-	-	-

S. Withdrawal/Early Withdrawal

1. **Describe how and when a subject may withdrawal from the study.** Once the subject completes the first session of the CBT-I, he will not be dropped from the study, unless they specifically request that they not be contacted, or the subject cannot be located for assessment by the 8-week follow-up. The subject may voluntarily withdraw from the study at any point in time. Subjects who are discontinued from the cognitive behavioral therapy intervention will continue to be followed in the study until the completion of the 8 weeks of intervention and the post-study follow-up at 3 and 6 months. The reason the subject is discontinued from the study and any referrals that are made are documented in the appropriate section of the subject's casebooks.
2. **Provide procedures for the orderly termination of participation by the participant and if any consequences would result from early withdrawal from the study.** The subject may be terminated from the research study by the investigator, without regard to his/her consent, under certain conditions. These conditions may include, if s/he does not comply with the recommendations of the research staff, including compliance with study related procedures on ≥3 consecutive office appointments; s/he reports ideas of harm to self or to anybody else with any intent and/or a plan. S/he will additionally be referred to the outpatient treatment program at the Addiction Recovery Unit of the CMCVAMC. Alternatively patient will be withdrawn from the study on successful completion of their study participation.

Subjects will be discontinued/withdrawn from the study if any of the following events occur:

- Any condition which the study psychiatrist finds CBT-I to be a hazard to the subject (i.e. patient seen to be agitated, onset of increasing paranoia, inability to follow through with recommendations and/or homework)
- Participant screens positive at baseline for moderate to severe obstructive sleep apnea (as seen baseline screening portable sleep monitor data), and is currently on not treatment for the obstructive sleep apnea
- Relapse to sustained heavy drinking during treatment as quantified at ≥ 5 standard drinks for men and ≥ 4 standard drinks for women less than 70 years of age, or a total of 14 drinks/ week in men and 7 drinks per week in women for ≥4 days a week and >1 week;

- Development of an inter-current medical illness or condition that requires a new hospital admission
- Emergence of another substance abuse problem which necessitates inpatient admission or a more aggressive treatment than provided by the protocol.
- Subject is incarcerated for more than a week.

Study participation can be restarted after consultation with the research physician for subjects who 1) return to treatment after a period of brief absence of less than 3 weeks, or 2) return to treatment after brief inpatient hospitalization of less than 2 weeks or additional outpatient treatment. Restarting study procedures is contingent upon clinical need and continuing to meet inclusion and exclusion criteria.

3. **Explain if survival data is required. If so, clarify how data will be obtained.** We will not be assessing for survival data in this pilot study. However we may consider looking at the survival data if there are a significant number of drop out of subjects from the study, with the end point of the survival analysis being the drop out date (i.e. total duration of participation in the study).
4. Not Applicable; subjects not recruited; chart review.

T. Risk/Benefit Assessment

1. Potential Study Risks

- 1.1. Describe and assess all of the following risks that may be associated with the research:
 - 1.1.1. Physical
 - a. Portable Sleep Apnea Monitoring: there may be discomfort associated with the use of nasal cannulas and sensors on the chest/abdomen;
 - b. Overnight Polysomnography: Sleeping in the CMCVAMC sleep laboratory with adhesive leads on the body may be associated with physical discomfort;
 - 1.1.2. Psychological
 - a. Sleep Restriction: patients may experience an increase in the daytime sequelae of insomnia as a result of this intervention (the scheduling of time in bed so as to equal average total sleep time). In the first few days of treatment this is likely to entail some sleep deprivation (~1 hour less sleep than is normal for the individual) and result in a transient increase in daytime sleepiness, fatigue, concentration problems, and irritability;
 - b. Data Collection during the Study: there may be discomfort associated with talking about family history of alcoholism, psychiatric issues and addiction-related issues. Furthermore, in some cases, the use of the sleep diaries and actigraphs may lead to (or be perceived as causing) a transient worsening of insomnia symptoms at home;
 - c. Relapse to Alcohol: there is a possibility that the transient "side effects" of CBT-I may lead some individuals to resort to occasional alcohol use and that such behavior may also lead to relapse (heavy drinking);
 - d. Use of Other Drugs: there is a possibility that the transient "side effects" of CBT-I may lead some individuals to start using other drugs while taking part in the study-related procedures;
 - e. Suicidal/Homicidal Ideation. While there is no evidence that CBT-I increases suicidal or homicidal ideation, it is a possible consequence of the transient sleep deprivation that occurs with CBT-I. That is, sleep deprivation may lead to decreased inhibition in the frontal brain areas, which may, in turn, lead to a failure to inhibit or cope with such thoughts, especially in vulnerable populations like those who suffer from alcoholism.
 - 1.1.3. Social. A decreased interest in affiliating with other people because of persisting insomnia or a transient increase in the insomnia secondary to the sleep restriction associated with the CBT-I.
 - 1.1.4. Economic. Time spent participating in the study may interfere with the subject's ability to seek employment or participate at his job.

- 1.1.5. Monetary. May be secondary to loss of time spent in participating in the study.
 - 1.1.6. Legal. An increase in the drowsiness may lead to potential risk of a motor vehicle accident.
 - 1.1.7. Loss of confidentiality a. there is a possibility that the subject's identifying data and/or study information may be viewed by non-study personnel.
 - 1.1.8. Assess the likelihood and seriousness of such risks. Although the risks associated with drowsy driving are serious, the likelihood of this risk is low. The likelihood of the other risks are variable, between a low to a moderate level, and specific to the Veteran's individual situation.
 - 1.1.9. Other. N/A
- 1.2. Specify what steps will be taken to minimize these risks.
- a. Portable Sleep Apnea Monitoring: While the use of nasal cannulas and sensors on the stomach and abdomen are required for this screening, subjects that experience discomfort during orientation will be provided (where possible) the opportunity to select from different types of cannulas and sensors .
 - c. Sleep Restriction: As noted above, this behavioral procedure is not without side effects (sleep loss and increases in the daytime symptoms of sleepiness, fatigue, concentration problems, and irritability). The subject will be made aware that "things will [and must] get worse before they get better" and that the transient worsening of symptoms is in the service of long-term gains. This said, in the rare cases where the procedure is viewed by the patient as intolerable, the protocol will be to either 1) re-assess the patient's basal sleep ability (conduct a second baseline assessment) or to substitute sleep compression⁵⁴ for sleep restriction. In addition, similar to our clinical care, we will counsel and monitor subjects at each of the follow-up visits for any excessive daytime drowsiness leading to drowsy driving, a risk factor for a motor vehicle accident, and we will review tips to avoid drowsy driving. If the patient does not wish to engage in these alternatives or the accommodations above do not increase the tolerability of the intervention, then the subject is (as always) free to withdraw from the study.
 - d. Data Collection during Initial Evaluation. Every attempt will be made to minimize the discomfort associated with disclosure of personal data. All of our staff are accustomed to and have a high degree of facility with the acquisition of sensitive information (e.g., drinking history). If, despite our staff's best efforts, the patient is unable to discuss issues that bear on their family and/or clinical history, they are free to not disclose this information and they are free to withdraw from the study. Further, if the patient's reluctance to share information precludes the acquisition of data that are critical to the conduct of the study, they will, at the PI's discretion, be asked to withdraw from the study. In the event that the subject feels they cannot tolerate completing daily sleep diaries or wearing the study actigraph, they will be told that such effects tend to be very transient. If the subject continues to find the collection of such data intolerable and/or is non-compliant, they will initially be assisted by the study-related staff in being compliant with the data collection through frequent reminders (as these data are central to the study). Despite frequent reminders, if they continue to remain non-compliant and at the PI's discretion, they may be asked to withdraw from the study.
 - e. Confidentiality: During the participation in this study, the patient will be assigned a 4-digit unique identification number. This number will not be derived from PHI of any sort (e.g., DOB, SSN, etc.) and will simply represent the study and the subject's recruitment number (e.g., 1001). Study numbers will be linked to subject identifiers in one spreadsheet that will be stored on the PI's password-protected VA online drive. These efforts make it very unlikely that the subject's identifying data and/or study

information may be viewed by non-study personnel. The data will now be captured and stored within the VA Redcap and stored in the secured VA servers.

- f. Relapse to the Drinking. All drinking behavior will be monitored. Monitoring will be based upon self-report items on the daily sleep diaries and clinical interviews by the principal investigator during the outpatient visits. These variables will be monitored for both research and clinical purposes. The research purpose is to determine how alcohol use varies with treatment for insomnia. The clinical purpose is to be able to determine if there has been a resumption of heavy drinking (four standard alcoholic drinks on any day or ≥ 14 drinks a week). If there is a resumption of sustained heavy drinking and this sustained heavy drinking places the subject at risk of medical, psychological or physical harm, then he will be withdrawn from the study, and a referral to the ARU or the inpatient unit, as deemed necessary for further treatment, will be offered to the participant
- g. Use of Other Street Drugs. Patients will be evaluated for the use of other street drugs through structured assessment instruments. Further, if there is a history of regular drug use, the subject will be regularly monitored with standard urine tests (note: this will be a condition for admittance into the study). If regular drug use is detected, the subject will be withdrawn from the study, and a referral to the ARU for further treatment will be offered to the participant.
- h. Suicidal/Homicidal Ideation. If the participant reports suicidal ideation with intent to hurt themselves, or if on evaluation, s/he is seen to be a danger to themselves or others, s/he will be referred immediately from the office to the Emergency Department of the CMCVAMC (CMCVAMC -ER). If s/he reports passive suicidal ideation, s/he will be monitored for any change during visits. S/he will also be offered a referral to the Addiction Recovery Unit of the CMCVAMC for further evaluation at the end of the study.

1.3. **If methods of research create potential risks, describe other methods, if any, that were considered and why they will not be used.** In the extreme situation where the risks cannot be mitigated with the above steps, and risk of participation in the study are considered to be greater than non-participation, the P.I. may withdraw the subject from the study and monitor him till the end of the study duration, along with any other additional clinical care that may be warranted.

1.4. **If chart review, breach of confidentiality is always a concern. Specify what steps will be taken to minimize these risks.** These will include the following: restriction of chart review to the P.I. and the study coordinator; storing the identifying information in locked drawers in locked office spaces; use of any of the 17-HIPAAA identifiers to communicate with research staff either over the phone or using the "do not forward" option of the VA email system; and discarding the patient related information into the designated shredding bins within the VA promptly after the information is reviewed or communicated with staff or the specific Veteran.

2. Potential Study Benefits

2.1. **Assess the potential benefits to be gained by the individual subject, as well as benefits that may accrue to society in general as a result of the planned work.** It is possible that the patients will not obtain any benefit from participation in this study. However, it is also possible that some of the participants may have an improvement in their insomnia after completion of their participation in the study. Some potential participants who screen positive for moderate to severe obstructive sleep apnea will be referred to the CMCVAMC Sleep Center for further evaluation and treatment for the

